3.2.7 Blinding/Masking

None. Though randomization will be concealed preventing allocation bias, it is impossible to blind caregivers or parents to the intervention. Interim results will be provided to the Data Safety Monitoring Committee (DSMC) with treatment assignments labeled only as group "A" and "B." We will record sodium and fluid intake as well as serum and urine sodium values in order to assess protocol compliance.

3.2.8 Primary Outcome

The change in somatic growth (weight gain, head circumference, and length) evaluated by the change in Z-score between 2 weeks of age and 36 weeks conceptual age or transfer from NICU. Weights will be extracted from the medical record, consistent study personnel will obtain the length (using a length board) and OFC.

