The change in somatic growth (weight gain, head circumference, and length) evaluated by the change in Z-score between 2 weeks of age and 36 weeks conceptual age or transfer from NICU.

Secondary Outcomes

- 1. The change in somatic growth (weight gain, head circumference and length) evaluated by the change in Z-score between 2 weeks of age and discharge or transfer from the NICU or 44 weeks corrected age (whichever occurs first)
- 2. Total body water and energy expenditure at 32 weeks corrected age.
- 3. Incidence and severity of bronchopulmonary dysplasia
- 4. Duration of mechanical ventilation
- 5. Need for supplemental oxygen
- 6. Use of diuretic therapy
- 7. Retinopathy of prematurity

SECTION 2. STATEMENT OF PROBLEM

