2.1 PRIMARY HYPOTHESES OR QUESTIONS

Aim 1. To determine the effects on somatic growth of adherence to a clinical practice algorithm guiding sodium supplementation as compared to current treatment practices in preterm infants.

Aim 2. To determine the effects on total body water and energy expenditure of adherence to a clinical practice algorithm guiding sodium supplementation as compared to current treatment practices in preterm infants.

Aim 3. To assess whether adherence to the algorithm impacts the incidence of secondary outcomes including, duration of mechanical ventilation, rates of bronchopulmonary dysplasia, duration of supplemental oxygen, severe retinopathy of prematurity (stage ≥3 or requiring treatment), length of hospitalization, and neurodevelopmental impairment.

Hypothesis 1. Use of this innovative algorithm to direct sodium supplementation will result in improved inhospital somatic growth (weight, length and head circumference) compared to standard treatment.

Hypothesis 2. Use of the clinical practice algorithm to guide sodium supplementation in premature infants will result in no differences in total body water but decreased energy expenditure compared to the control group.

Hypothesis 3. Use of the algorithm will not negatively impact the incidence of common neonatal morbidities, including duration of mechanical ventilation, rates of bronchopulmonary dysplasia, duration of supplemental oxygen, severe retinopathy of prematurity, length of hospitalization, and neurodevelopmental impairment.

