5.2.2 Statistical analysis

All analyses will be performed on an intent-to-treat basis. The primary analysis (and all analyses examining outcomes by treatment) will be adjusted for the stratification variable of gestational age. Since the primary outcome is continuous, linear regression will be used to estimate the adjusted mean difference in growth between the two treatment groups. Similarly, for secondary outcomes, linear regression will be used for continuous outcomes and robust Poisson regression for binary or categorical outcomes to obtain adjusted relative risk estimates for the treatment effect.

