5.2.3 Sample size and power estimates

Sample size and power calculations for this study are based upon the primary outcome of differences in weight gain between the two groups of infants. Using data from our recently completed analysis, in which infants 26 – 29 6/7 weeks gestation treated according to the algorithm were compared with historical controls, and based upon identifying a difference in weight Z-score of 0.25 at 36 weeks postmenstrual age, using a SD of 0.4 with an alpha = 0.05 and power of 0.8, we calculate we will need a total sample size of 82 patients (41 per group). With regards to the secondary outcome of EE, and based upon published data of EE estimated in preterm infants using the DLW method, a sample size of 41 patients per group will allow us to detect a 6% difference in EE, assuming an alpha = 0.05 and a power of 0.80. With regards to TBW, and based upon data from these same investigators who report a mean TBW of 80.8% body weight, with SD of 3.1%, this sample size will allow us to detect a difference in TBW of 2.0% between groups, assuming an alpha = 0.05 and a power of 0.80. To acknowledge for study drop out, we will plan to enroll up to 90 patients (plus 90 mothers for chart review).

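### Three growth measures are named as primary, but the trial is sized on weight alone at the full alpha of 0.05, and no rule says which measure decides the trial

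*Combined protocol and SAP*

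**What the plan says.** The places that bear on the deciding test do not agree.

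- **Section 3.2.8, Primary Outcome:** "The change in somatic growth (weight gain, head circumference, and length) evaluated by the change in Z-score between 2 weeks of age". The interval ends at 36 weeks or at transfer from the NICU. The Primary Outcome entry in the Section 1 abstract says the same.
- **Section 2.1, Hypothesis 1:** the algorithm "will result in improved inhospital somatic growth (weight, length and head circumference) compared to standard treatment". The three measures are joined by 'and'.
- **Section 5.2.2, Statistical analysis:** "Since the primary outcome is continuous, linear regression will be used to estimate the adjusted mean difference in growth between the two treatment groups". The outcome is singular, and the growth variable is not identified.
- **Section 5.2.3, Sample size:** the calculation is "based upon the primary outcome of differences in weight gain between the two groups of infants". The target is a weight Z-score difference of 0.25 at 36 weeks, and the remaining inputs are "using a SD of 0.4 with an alpha = 0.05 and power of 0.8". The result is 82 patients, 41 per group. No effect size or SD is given for head circumference or length.

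The only other remark on alpha is in section 5.3, and it concerns the interim safety looks. No section ranks the three measures, combines them, splits alpha between them, or says whether one or all must be significant.

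**The concern.** A confirmatory trial needs one rule, fixed in advance, that turns its results into success or failure. Here three rules can be read from the plan: weight decides, any of the three suffices, or all three are needed. They have different error rates and different power, and only the first matches the sample-size paragraph.

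Suppose weight shows no difference and length is significant at 0.05. The definition in 3.2.8 would let that be reported as a positive primary result; the wording in 5.2.3 would not. Because the plan does not settle the matter, the deciding measure could be picked after the results are known. The trial is also unmasked (section 3.2.7), and section 2.2 expects it to inform practice, so the choice should not be left open.

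**Working it through.** **Inputs from the documents**
- Difference 0.25 in weight Z-score, SD 0.4, alpha 0.05, power 0.8, 41 per group (section 5.2.3).
- 1:1 allocation (section 3.2.3).
- Sidedness is not stated.

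**Assumptions, because the documents are silent**
- A common pairwise correlation ρ between the three test statistics, from 0 to 0.9.
- For the all-three rule, the same standardised effect on each measure as on weight.

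**Step 1: reproduce the plan's figure (weight alone)**
- Standardised effect: 0.25/0.4 = 0.625.
- n per arm = 2 × (1.960 + 0.842)² × 0.4² / 0.25² = 40.2, rounded up to 41, so 82 in total. This matches the plan.
- A one-sided test would need only 32 per arm, so the plan's figure is two-sided.
- Expected test statistic at 41 per arm: 0.625 × √(41/2) = 2.830. Power = Φ(2.830 − 1.960) = 80.8%; the t-test gives 79.8%.

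The sizing is therefore sound for one test of weight at the full two-sided 0.05.

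**Step 2: any one of three counts, each tested at two-sided 0.05**
- With independent measures, the chance of at least one false positive is 1 − 0.95³ = 14.3%.
- With correlated measures it is 1 − P(|Z₁|, |Z₂| and |Z₃| all < 1.960) for a trivariate normal with common correlation ρ.

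**Step 3: all three required, each at two-sided 0.05**
- No alpha adjustment is needed, but power is the joint probability that all three statistics exceed 1.960 when each has mean 2.830.
- With independent measures this is 0.808³ = 52.7%.

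| ρ (assumed) | Any of three: false-positive rate | All three: power at 41 per arm |
|---|---|---|
| 0 | 14.3% | 53% |
| 0.5 | 12.5% | 62% |
| 0.7 | 10.9% | 67% |
| 0.9 | 8.4% | 73% |

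The power column uses the normal approximation; t-tests give roughly 51% to 72%.

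**Step 4: the cost of keeping any-of-three with error controlled**
- Bonferroni alpha: 0.05/3 = 0.0167, critical value 2.394.
- n per arm = 2 × (2.394 + 0.842)² × 0.4² / 0.25² = 53.6, so 54 per arm and 108 in total (56 per arm and 112 by t-test).
- Power for weight at the planned 41 per arm would fall to 66.9% (65.0% by t-test).

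**The case against.** The strongest reply is that weight was plainly meant to decide. Section 5.2.3 calls weight gain the primary outcome in so many words, section 5.2.2 speaks of one outcome and one regression, the definition lists weight first, and the preliminary growth result in section 2.2 is a change in weight Z-score. On that reading the alpha, the power and the 82 patients are all correct, and the fault is loose wording. This is good evidence of intent, and the fix below adopts it. It does not remove the conflict, because the formal definition in 3.2.8 and the abstract still makes head circumference and length primary, and no section demotes them. The growth item among the secondary outcomes does not do so either: it covers the same three measures at a later end point.

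Three objections to the figures also have some force.

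- **Direction.** The 8% to 14% counts false positives in either direction, whereas Hypothesis 1 predicts improvement. The chance of at least one false finding in favour of the algorithm is about 4.2% (ρ = 0.9) to 7.3% (ρ = 0), against 2.5% for a single test. It is smaller but still inflated.
- **Borrowed effects.** The all-three power gives head circumference and length the effect assumed for weight. True joint power could lie outside 53% to 73%. It cannot exceed the power for weight alone, which is about 80% at 41 per arm.
- **Enrolment.** Up to 90 infants may be enrolled. If all 45 per arm were analysed, all-three power would be about 60% to 77%, still under 80%.

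Finally, that the deciding measure might be chosen late is a possibility the plan leaves open. Nothing in the documents suggests it is intended.

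**Conclusion.** The concern holds. The plan contradicts itself on which test decides the trial, and this should be settled before any outcome analysis. The sample-size arithmetic is correct, but it supports the stated error and power only if weight alone decides. Under an any-of-three rule the two-sided error is about 8% to 14% instead of 5%; under an all-three rule the power is about 53% to 73% instead of 80%. Those ranges are conditional on rules the plan does not state and on the assumed correlations and, for power, equal effects. The contradiction itself rests on none of these assumptions.

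**What to change.** In the abstract's Primary Outcome, section 3.2.8 and section 5.2.2, name the change in weight Z-score as the single primary outcome, keeping the present start and end points. State in 5.2.2 that the adjusted regression of this variable is the one test that decides the trial, at two-sided 0.05.

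Make head circumference and length over the same interval key secondary outcomes. Test each at 0.05 in an order that the sponsor fixes in advance, and only if weight and any measure earlier in the order are significant. If the sequence stops, report the remaining measures as estimates with confidence intervals. This controls the error rate across all three. Hypothesis 1 and the later-time-point growth outcome can stay as they are.

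The sponsor could instead require all three measures or split alpha, but either choice would need a new sample-size calculation, with effect sizes and SDs for head circumference and length that the documents do not give.

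The recommended change costs a few lines of text and no patients: 82 evaluable and up to 90 enrolled still stand. Its drawback is that a benefit on head circumference or length cannot be claimed as confirmed if weight fails.

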For infants receiving >80 ml/kg/d of enteral feedings: The designated amount of sodium will be added to the feedings (sole route of supplementation) or provided by a combination of enteral and parenteral route. When provided enterally, sodium will be administered in equally divided quantities with every other feeding, (i.e., 4 feedings each day for infants fed every 3 hours, 3 feedings each day for infants fed every 4 hours). Enteral supplemental sodium may be administered in the form (sodium chloride, sodium acetate, sodium citrate, sodium bicarbonate, or any mixture) chosen by the care team.

3.2.5 Data collection:

Growth and nutrition data, including fluid, caloric, protein, carbohydrate and lipid intakes and weight, will be abstracted from the infants' medical records and entered on to study data collection instruments. Standardized data collection forms will be used for collection all clinical outcome data and entered into a REDCap data base as described below. Other variables will be recorded on data forms created for this trial. The potential confounding variables include but are not limited to:

- Maternal demographic variables: maternal age, maternal education level, maternal race/ethnicity, maternal health issues, presence of chorioamnionitis, preeclampsia, reason for preterm delivery
- Labor and delivery: rupture of membranes, steroid exposure, antibiotics, mode of delivery
- Infant health demographic variables: gestational age at birth, birthweight, length, sex, small for gestational age status, parity, Apgar scores, delivery room resuscitation, initial respiratory support, blood pressure, body temperature, pH, PaO2, FiO2.
- Infant neurologic and medical morbidity: death, presence and severity of intracranial hemorrhage, presence of periventricular leukomalacia, seizures, patent ductus arteriosus, early and late onset sepsis, bronchopulmonary dysplasia, retinopathy of prematurity (stage ≥3 or requiring treatment), age at final tracheal extubation, length of hospital stay, duration of need for supplemental oxygen and diagnosis of hypertension as defined as need for scheduled antihypertensive agents.

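### The head-circumference part of the primary outcome counts any rise in OFC Z-score as growth, with no prespecified handling of heads enlarged by post-hemorrhagic ventricular dilatation

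*Combined protocol and SAP*

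**What the plan says.** Section 3.2.8 (Primary Outcome) gives one definition for weight, OFC and length: "The change in somatic growth (weight gain, head circumference, and length) evaluated by the change in Z-score between 2 weeks of age". The window closes at 36 weeks, or at transfer out of the unit. The section sets no upper limit on OFC change and no rule for abnormal head enlargement. Hypothesis 1 in section 2.1 fixes the direction of benefit: the algorithm "will result in improved inhospital somatic growth (weight, length and head circumference) compared to standard treatment".

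The exclusion criteria (section 3.1.2) cover major congenital anomalies and several renal and fluid conditions, but not acquired intracranial hemorrhage. Section 3.2.5 (Data collection) lists "presence and severity of intracranial hemorrhage" among the potential confounders to be recorded. It names neither ventricular dilatation nor hydrocephalus.

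Under section 5.2.2 all analyses are intent-to-treat. The primary analysis is a linear regression that estimates a mean difference and "will be adjusted for the stratification variable of gestational age". No other covariate and no sensitivity analysis is named. Randomization (section 3.2.3) is 1:1, stratified by gestational age only.

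Section 5.2.3 sizes the trial on weight: the calculation is "based upon identifying a difference in weight Z-score of 0.25 at 36 weeks postmenstrual age". The SD (0.4), alpha (0.05) and power (0.80) given there belong to the same weight calculation. The section gives no effect size or SD for OFC.

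**The concern.** A higher OFC Z-score is meant to indicate better growth, and sections 2.2 and 3.2.5 show why that matters: growth is valued for its link with neurodevelopment, and hemorrhage is expected often enough in infants of 25 to 29 weeks to be collected. If ventricles dilate after a severe hemorrhage during the outcome window, the head enlarges for a reason that is not growth. Applied literally, an infant without hemorrhage whose OFC Z-score goes from -1.0 to -0.9 scores +0.1. An invented infant with dilatation who goes from -1.0 to +1.1 scores +2.1 and ranks among the best growers.

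A linear regression on means gives such values full weight. With about 41 infants per arm, a few of them can widen the confidence interval for OFC, and an uneven split between arms can move the estimate. The plan records hemorrhage as a potential confounder but does not use it in the model. The trial is also unmasked (section 3.2.7), so a decision to set large heads aside after seeing the data would be open to the charge of selection.

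**Working it through.** **1. The plan's own figure.** Inputs from section 5.2.3: difference 0.25, SD 0.4, alpha 0.05, power 0.80, all for weight. The normal formula gives n per arm = 2 × (1.960 + 0.842)² × (0.4/0.25)² = 40.2, rounded up to 41, or 82 in total. This matches the plan and implies a two-sided test. The t-test power at 41 per arm is 0.798.

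**2. Inputs that the documents do not give.** Everything here is an assumption:
- fraction affected p: 2%, 4%, 6%
- added OFC change x: +1.5, +2.0, +2.5 Z
- OFC SD among unaffected infants: 0.4 (borrowed from weight), with 0.8 as an alternative
- OFC difference of interest: 0.25 (borrowed from weight)

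**3. Loss of precision.** If a fraction p is shifted by x, SD = √(SD₀² + p(1−p)x²). Power is for a difference of 0.25, two-sided t-test, 41 per arm.

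| p, x | p(1−p)x² | SD (SD₀ = 0.4) | Power | SD (SD₀ = 0.8) | Power |
|---|---|---|---|---|---|
| none | 0 | 0.400 | 0.80 | 0.800 | 0.29 |
| 2%, +1.5 | 0.0441 | 0.452 | 0.70 | 0.827 | 0.27 |
| 4%, +2.0 | 0.1536 | 0.560 | 0.52 | 0.891 | 0.24 |
| 6%, +2.5 | 0.3525 | 0.716 | 0.35 | 0.996 | 0.20 |

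The loss depends heavily on the unknown OFC SD. It is large at 0.4 and small at 0.8, where power is already low.

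**4. Chance imbalance.** One extra affected infant in an arm moves the difference by x/41, that is 0.037, 0.049 or 0.061 Z. An imbalance of two moves it by 0.07 to 0.12, and of three by 0.11 to 0.18. From two independent Binomial(41, p) counts, the arms differ by two or more affected infants with probability 0.21, 0.38 and 0.47 at p = 2%, 4% and 6%.

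**5. What a shift of 0.25 would need.** 0.25 × 41/x = 6.8, 5.1 or 4.1, so an imbalance of 7, 6 or 5 infants at x = 1.5, 2.0 or 2.5. The most favorable case for this (p = 6%, x = 2.5) has probability 0.037 in either direction; every other combination has less.

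**6. What a baseline covariate recovers.** Take p = 4%, x = +2 and SD₀ = 0.4, and assume that all affected infants come from a fraction q with severe hemorrhage before baseline. With r = p/q, the residual SD is √(0.16 + q·r(1−r)·x²). For q = 6% this is 0.462 (power 0.68); for q = 10% it is 0.506 (power 0.60). Without the covariate power is 0.52.

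**The case against.** The strongest reply is that the plan makes no power claim for OFC. The 0.25 and the SD of 0.4 belong to weight ("Sample size and power calculations for this study are based upon the primary outcome of differences in weight gain between the two groups of infants"), so the fall from 0.80 starts at a level that the plan never promised. This stands, and the power figures above are illustrations only.

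A reader might infer that enlarged heads would swamp an effect of 0.25, or that an imbalance of two or three infants could create or hide one. The documents do not support that. They give no OFC effect to swamp, and two or three infants move the difference by 0.07 to 0.18 Z under the assumptions used. A shift of 0.25 has at most about a 4% chance.

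A reader might also infer a bias that presents brain injury as a benefit of the algorithm. Allocation is randomized, and nothing in the documents says that the intervention changes the rate of dilatation. Imbalance is as likely to count against the algorithm as for it.

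It can also be said that hemorrhage severity is collected, so a sensitivity analysis could be run anyway. That is partly true. Section 5.2.2 does not prespecify one, section 3.2.5 asks for no diagnosis date, and dilatation is not named as a data item.

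**Conclusion.** The point holds as a gap in the OFC analysis. Any rise counts as growth, infants with severe hemorrhage stay in, and neither a covariate nor a sensitivity analysis deals with pathological enlargement. That much follows from the text. That dilatation can follow hemorrhage within the outcome window is clinical background which the documents do not discuss.

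The harm is lost precision and symmetric chance imbalance in one of three primary components. The documents do not allow its size to be fixed: over the assumed range it runs from a power loss of about 0.02 (OFC SD 0.8, 2% affected, +1.5 Z) to about 0.45 (OFC SD 0.4, 6% affected, +2.5 Z). The weight comparison, on which the trial is sized, and the length comparison are not directly touched. The change is worth making because it is cheap and has to be settled before the data are seen.

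**What to change.** In section 5.2.2, for OFC only:

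1. Add severe intracranial hemorrhage diagnosed before the 2-week baseline as a covariate. Record the diagnosis date on the form, so that the covariate is a true baseline value.
2. Record ventricular dilatation as one chart item, and prespecify a supportive OFC estimate without affected infants. Report it beside the intent-to-treat estimate, labelled as conditioning on a post-randomization diagnosis.

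The supportive estimate should have no veto over the intent-to-treat result. A rule that the two must agree would let a subset chosen after randomization, in an unmasked trial, overrule a primary component. Weight and length analyses stay as they are.

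The cost is a diagnosis date, one chart item, a short addition to the analysis text and one extra model. The drawback is that the supportive estimate is not intent-to-treat and must be read as such.

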3.2.9 Secondary Outcomes

- 1. The change in somatic growth (weight gain, head circumference and length) evaluated by the change in Z-score between 2 weeks of age and discharge or transfer from the NICU or 44 weeks corrected age (whichever occurs first).
- 2. Total body water and energy expenditure at 32 weeks corrected age
- 3. Incidence and severity of bronchopulmonary dysplasia
- 4. Duration of mechanical ventilation
- 5. Need for supplemental oxygen
- 6. Use of diuretic therapy

7. Retinopathy of prematurity

SECTION 4. ADVERSE EVENTS AND REPORTING

